1.0 PROTOCOL SUMMARY AND/OR SCHEMA

1.1 Background and Rational

The standard first line therapy for patients with multiple myeloma includes 2 phases: An *initial* treatment, which usually consists of a combination of several drugs given for 3 to 6 cycles, followed by *consolidation* with autologous stem cell transplantation using high dose melphalan (HDM/ASCT). In recent years, the HDM/ASCT consolidation phase has often been replaced by a continuous phase, in which some or all the drugs used as initial treatment are continued beyond the initial 3-6 cycles. Lenalidomide is often chosen for this continuous phase, due to its convenient oral administration, becoming a continuous/maintenance treatment. In additions, two major large studies recently presented at the ASCO and ASH meetings in 2010, have emphasized the role of maintenance therapy with low dose lenalidomide after HDM/ASCT. Both studies have shown a statistically significant improvement in the progression free survival for patients receiving maintenance therapy with low dose lenalidomide after HDM/ASCT. Although the improvement in overall survival is currently not fully established (there is a trend toward increased OS), it is clear at this time that maintenance therapy post HDM/ASCT has been widely adopted by myeloma experts. Therefore, most patients who initiate therapy for multiple myeloma will remain on maintenance therapy with low dose lenalidomide as part of their initial treatment.

However, most of these patients will eventually progress while on lenalidomide therapy. Patients with “symptomatic progression of disease (POD)” defined by new symptomatic bone lesions, progressive anemia, hypercalcemia, or progressive renal failure attributable to the multiple myeloma, usually in association with a rise in the serum or urine paraprotein, will require re-induction therapy with combination chemotherapy to prevent further organ deterioration. However, the subset of patients with “serologic or asymptomatic POD”, i.e. whose only evidence of disease progression is an increase in the paraprotein level by $\geq 25\%$ above plateau baseline, have a variable natural history with many patients not showing symptomatic progression for months. Based on the results of the initial phase I trial of lenalidomide in which higher responses were seen with higher doses of lenalidomide, we hypothesize that in patients relapsing on lenalidomide maintenance doses of 5-15 mg orally daily, the disease could be brought under control by increasing the dose of lenalidomide (intensification) to 25 mg. However, the response rates and tolerance of lenalidomide dose intensification in the setting of lenalidomide maintenance is unknown, which is the basis for the proposed clinical trial.

For the purpose of clarity, the term asymptomatic POD will be used henceforward to designate serologic only POD, while symptomatic POD will be used to designate POD associated with progression of organ damage.

1.2 Study Design and Objectives

The proposed study is designed as a Phase II, multi-center trial of lenalidomide intensification in patients with asymptomatic POD while on low dose lenalidomide maintenance after HDM/ASCT or as continuous/maintenance therapy after initial treatment. The primary objective of this trial is to determine the overall response rate (ORR) at 6 months and the toxicity of lenalidomide administered at a dose of 25 mg orally, days 1 to 21 of a 28 day-cycle, without or with dexamethasone added after 2 cycles, in patients with multiple myeloma found to have asymptomatic POD while on a maintenance lenalidomide dose of 15 mg daily or less.

1.3 Patients Eligibility

Patients with multiple myeloma with evidence of *asymptomatic POD* while on lenalidomide maintenance post HDT/ASCT or on continuous/maintenance therapy as part of first line therapy will be eligible to participate in this trial. Patients will need to have progression of disease documented as defined by modified IMWG criteria and will have no evidence of progression of organ damage (progression of severe anemia, renal failure, hypercalcemia, bone disease).

1.4 Treatment Intervention

After registration patients will begin therapy with lenalidomide 25 mg daily, 21 days out of a 28 day schedule. All patients will be evaluated monthly after every cycle. The dose will be adjusted downward in response to side effects and according to specific guidelines. Symptomatic POD occurring at any time during the study will result in removal of the patient from the study. After 2 cycles of lenalidomide, patients with at least stable disease (SD) will continue lenalidomide indefinitely until asymptomatic POD, at which time dexamethasone will be added at a dose of 40mg weekly. On the other hand, patient with asymptomatic POD after 2 cycles of lenalidomide will have dexamethasone added at a dose of 40 mg weekly. Patients with any type of POD after any cycle that includes dexamethasone will be taken off study. Patients can remain on study on lenalidomide or lenalidomide/dexamethasone indefinitely as long as they do not have POD as stated above and they tolerate the treatment.

1.5 Outcome Measurements

The response to treatment intervention will be measured using a modified version of the widely accepted Uniform International Response Criteria in multiple myeloma. To determine response, patients' disease will be assessed at the beginning of every cycle and compared to the new baseline established within two weeks prior to initiation of lenalidomide intensification.

1.6 Statistical Considerations

The focus of this study is to estimate the overall response rate (\geq PR) to lenalidomide

[figure not shown]

MEMORIAL SLOAN-KETTERING CANCER CENTER IRB PROTOCOL

IRB#: 11-107A(12)

intensification with or without dexamethasone at 6 months. A single stage design that differentiates between response rates of 15% and 30% will be used to assess efficacy of lenalidomide intensification with or without dexamethasone. The probabilities of a type I error (falsely accepting a non-promising therapy) and type II error (falsely rejecting a promising therapy) are set to 0.10 and 0.10, respectively. The null hypothesis response rate is based on the response rate to the standard of care therapy in patients previously exposed to thalidomide who have relapsed or refractory disease. A total of 53 patients will be accrued. At the conclusion of the study, if a least 12 of the 53 patients respond by 6 months the treatment will be declared a success.

1.7 Study Schema

2.0 OBJECTIVES AND SCIENTIFIC AIMS

Primary objective:

- To determine the overall response rate (CR, VGPR, PR, and MR) after 6 months of lenalidomide intensification administered initially at a dose of 25 mg orally days 1 to 21 of a 28 day-cycle, with or without the addition of dexamethasone, in patients with multiple myeloma found to have *asymptomatic* progression of their disease while on maintenance lenalidomide dose of 15mg mg daily or less.

Secondary objectives:

- To determine rates of \geq Grade 2 toxicity according to the Common Terminology Criteria for Adverse Events (CTCAE) Version 4.0
- To determine the overall response rate (CR, VGPR, and PR) at 6 months from initiation of lenalidomide intensification therapy of lenalidomide given as a single agent.
- To determine progression free survival: The PFS is defined as the time from registration to relapse/progression, death, initiation of non-protocol anti myeloma therapy, loss to follow up or end of study whichever comes first.
- To determine OS: The OS is defined as the time from registration to death, loss to follow-up or the end of the study, whichever comes first. Patients alive at the time of last observation are considered censored.

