3.2.1 Rationale for Lenalidomide Intensification Dose

The maximum tolerated dose (MTD) of lenalidomide as a daily dose is 25 mg with dose-limiting toxicity (DLT) being grade 3/4 myelosuppression. The Phase I trial of single agent lenalidomide demonstrated higher response rates with increasing dosage with 20%, 66%, and 69% of patients having at least a minimal response when receiving 10 mg, 25 mg, and 50 mg respectively³². Based on the pharmacokinetic data of the phase I trial, and the favorable toxicity profile observed, a randomized Phase II study has been reported that examined a higher dose with an interrupted schedule: 15 mg twice daily versus 30 mg daily on a 3 weeks on / 1 week off schedule³³. This study examined 70 patients randomized to the two schedules. Fifty-seven patients were analyzed for toxicity and 46 for response. In this heavily pre-treated group of patients, 24% had a CR or PR or minimal response and only 16% had progressive disease. One patient developed grade 3 neuropathy. The most common grade 1 and 2 toxicities were fatigue, self-limited rash, muscle cramps and diarrhea. Grade 3 or 4 myelosuppression was seen in 26% (n=15) of patients. Eleven of these 15 patients had undergone a prior autologous transplant; most (n=11) were on the 15 mg twice a day dose. The daily dosing schedule was felt to be more favorable based on its toxicity profile and simplicity of administration with best opportunity for compliance. There was no evidence that an interrupted schedule enhanced long-term tolerability or response. Thus, there is data supporting the dose related response to lenalidomide and its optimal efficacy/tolerability ratio with 25 mg given daily for 21 days every 28 days.

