With the results of CALGB100104 and IFM05 it is likely that many patients will now be relapsing on lenalidomide maintenance which consists of lower doses of lenalidomide without dexamethasone. Based on the results of the phase I study of lenalidomide we hypothesize that intensifying the dose of lenalidomide could potentially re-establish control of the disease in up to 30% of myeloma patients with asymptomatic relapses, therefore saving the use of other agents for future use.

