14.0 BIOSTATISTICS

The primary objective of this study is to estimate overall response rate (\geq PR) to lenalidomide intensification with or without dexamethasone at 6 months. A single stage design that differentiates between response rates of 15% and 30% will be used to assess efficacy of lenalidomide intensification with or without dexamethasone.

The probabilities of a type I error (falsely accepting a non-promising therapy) and type II error (falsely rejecting a promising therapy) are set to 0.10 and 0.10, respectively. The null hypothesis response rate is based on the response rates ranging from 12.5% to 16.4% to the standard of care therapy in patients previously exposed to thalidomide who have relapsed or refractory disease (reference Webber and Dimopoulos papers^{38,39}). A total of 53 patients will be accrued. At the conclusion of the study, if a least 12 of the 53 patients respond by 6 months the treatment will be declared a success. At the end of the study, the response rate will be estimated and a confidence interval will be constructed.

We expect to accrue 53 patients in two years with approximately 10-15 patients accrued from MSKCC and the remaining patients accrued from the other centers.

The incidence of toxicities of grade 2 or higher toxicities (CTCAE version 4.0), the incidence of probable viral fungal and bacterial infections, and the incidence of treatment-related mortality, i.e., from causes other than relapse or progression, will be recorded for each patient after each cycle and at the end of study visit. Safety data will be described in a variety of ways, both graphically and in tabular form.

Progression free survival is defined as the time from treatment initiation to relapse/progression, death, initiation of non-protocol anti myeloma therapy, or last follow-up. Overall survival is defined as time from treatment initiation until death or last follow-up. Progression free and overall survival will be estimated using the Kaplan-Meier method.

We will estimate the response rate (CR, VGPR, and PR) by 6 months from initiation of lenalidomide intensification of lenalidomide given as single agent. For this calculation, patients who have asymptomatic progression after 2 cycles of lenalidomide and receive dexamethasone will be considered failures.

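### The primary response rate counts minor response in Section 2.0 but is PR or better in Sections 1.6 and 14.0, where the 12-of-53 success rule is set

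*Combined protocol and SAP*

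**What the plan says.** Section 2.0 (primary objective) reads "To determine the overall response rate (CR, VGPR, PR, and MR) after 6 months of lenalidomide intensification". This is the only place where MR counts as a response for this trial's primary endpoint.

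Section 14.0 reads "The primary objective of this study is to estimate overall response rate (\geq PR) to lenalidomide intensification", and Section 1.6 reads "The focus of this study is to estimate the overall response rate (\geq PR) to lenalidomide". Both sections then give the design: a single-stage test of 15% against 30%, type I and type II error each set at 0.10, 53 patients, and success if at least 12 respond by 6 months.

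Other passages that bear on the point:

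- Section 1.2 names the overall response rate at 6 months as the primary objective without defining response.
- Section 12.0 makes MR a separate category below PR. In serum terms, MR is a 25% to 49% reduction in monoclonal protein and PR is at least 50%.
- The secondary single-agent objective in Section 2.0 omits MR: "To determine the overall response rate (CR, VGPR, and PR) at 6 months from initiation of lenalidomide intensification therapy". Section 14.0 defines that secondary rate in the same way.
- Section 14.0 bases the null on "response rates ranging from 12.5% to 16.4% to the standard of care therapy" and does not say which response categories those rates include.
- Section 3.2.2.1 draws on the phase I study for its hypothesis that "intensifying the dose of lenalidomide could potentially re-establish control of the disease in up to 30% of myeloma patients with asymptomatic relapses". Section 3.2.1 reports that study as "20%, 66%, and 69% of patients having at least a minimal response when receiving 10 mg, 25 mg, and 50 mg respectively".

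**The concern.** Two sections of the current text each state the primary objective, and they count different patients as responders. The trial's conclusion rests on a single comparison of the responder count with 12, so the definition can decide the verdict. Suppose 9 patients reach PR or better and 4 more reach MR. Under Section 14.0 the count is 9/53 and the treatment fails. Under the Section 2.0 definition it is 13/53 and the treatment succeeds. In a single-arm trial with both definitions in the protocol, that choice could be made after the data are seen.

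The error rates are also tied to one definition only. The 15% and 30% rates appear only in the sections that use PR or better. If the same cutoff is applied to a count that includes MR, the stated 0.10 type I error has no support, because no null rate for that count is given.

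**Working it through.** **Inputs.** From Sections 1.6 and 14.0: n = 53, success at r = 12 or more, p0 = 0.15, p1 = 0.30, both error rates 0.10. From Section 14.0: the cited null range, 12.5% to 16.4%. The documents give no MR rate, so every MR increment below is an assumption.

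**Step 1: reproduce the plan's design.** With X binomial(53, p), the probability of success is P(X ≥ 12 | p).

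- Type I error: P(X ≥ 12 | 0.15) = 0.0907.
- Power: P(X ≥ 12 | 0.30) = 0.9094.
- A cutoff of 11 gives type I error 0.1622. A cutoff of 13 gives power 0.8463.
- 12/53 is the smallest exact single-stage design that meets 0.10/0.10 for 15% versus 30%.

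The design arithmetic is correct. It would be equally correct for any response definition that carried those two rates, so it is not evidence of which definition was intended.

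**Step 2: the room left for MR.** Solving P(X ≥ 12 | p) = 0.10 gives p = 0.1526. From a null of 15%, that leaves about 0.26 of a percentage point before the type I error exceeds 0.10. Over the cited null range, the type I error is 0.0282 at 12.5% and 0.1489 at 16.4%.

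**Step 3: apply the same cutoff to a count that includes MR.** Let the true PR-or-better rate be 15% and let m be the assumed additional proportion whose response is MR. False success then has probability P(X ≥ 12 | 0.15 + m). Every PR-or-better responder is also a responder when MR counts, so the larger count can never be below the smaller one. The two definitions therefore give opposite verdicts with probability P(X ≥ 12 | 0.15 + m) − P(X ≥ 12 | 0.15).

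| Assumed m | Rate counting MR | P(12 or more) | P(opposite verdicts) |
|---|---|---|---|
| 0 | 15% | 0.0907 | 0 |
| 1 point | 16% | 0.1305 | 0.0398 |
| 2 points | 17% | 0.1791 | 0.0884 |
| 5 points | 20% | 0.3670 | 0.2763 |
| 10 points | 25% | 0.7039 | 0.6133 |

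The definition matters less if the treatment works as hoped. At a true PR-or-better rate of 30% with 5 added points, the opposite-verdict probability is 0.9818 − 0.9094 = 0.0724.

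**Step 4: what an MR-inclusive design would need.** The nulls are assumed, with the target set 15 points higher in each case.

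| Assumed null | Cutoff at n = 53 | Type I error | Power | Smallest 0.10/0.10 design |
|---|---|---|---|---|
| 17% | 14 | 0.056 | 0.846 | 14/57 |
| 20% | 15 | 0.094 | 0.880 | 17/61 |
| 25% | 18 | 0.092 | 0.850 | 21/64 |

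At 53 patients none of these reaches the planned power of 0.90.

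**The case against.** The best defence is that the intent is clear enough. The hypotheses, error rates, sample size and success rule appear only where response means PR or better, and Section 14.0 calls that version the primary objective. The secondary single-agent rate leaves MR out. The stable-disease definition in Section 12.0 does not list MR among the categories that rule out stable disease, which fits a plan where MR is not a response, though it could be a drafting slip. On this view the MR in Section 2.0 is a stray entry, and the type I error problem arises only if someone carries Section 14.0's cutoff over to Section 2.0's definition. The MR increments are hypothetical, the opposite-verdict figures are worst near the null, and a null of 12.5% would leave about 2.8 points of room (15.26 − 12.5).

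Much of this stands. PR or better is the more natural reading, and the probabilities show sensitivity, not a mistake in the plan's calculation. It does not remove the contradiction. No passage says that Section 14.0 takes precedence. Section 2.0 includes MR in the primary objective and omits it from a secondary objective in the same list, which can also be read as deliberate. The evidence from the 30% hypothesis is weak in either direction: it names no response category, and although the phase I rates it draws on are for at least minimal response, the 25 mg figure there is 66%, not 30%. The room at 12.5% is offset by the upper end of the cited range, where the type I error is already 0.1489 before any MR is added. If Section 14.0 does govern, Section 2.0 is wrong and still has to be corrected.

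**Conclusion.** The concern holds and must be fixed. The protocol gives two incompatible definitions of its primary endpoint, and the difference can reverse its only success decision. The 12-of-53 rule is valid for PR or better at 15% versus 30%. For the MR-inclusive rate in Section 2.0 the true type I error is unknown, because no null rate is given. It would exceed 0.10 at any null above about 15.26%. The values of 0.13 to 0.70 for 1 to 10 added points assume a PR-or-better null of exactly 15% and MR rates that the documents do not supply. The finding itself rests on the conflicting text and not on those assumptions.

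**What to change.** Use one primary definition throughout. The simplest change is to amend the primary objective in Section 2.0 to an overall response rate of sCR, CR, VGPR and PR, matching Sections 1.6 and 14.0 and the secondary single-agent endpoint, and to report MR descriptively outside the 12-of-53 decision. This is a wording amendment. The sample size and cutoff stay as they are, and no patients or data are added. The price is a headline rate lower than one that counts MR.

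If MR is truly meant to count, state and justify a null and target for that definition and recalculate the cutoff and sample size. With the assumed nulls tabulated above, that means 57 to 64 patients, or 4 to 11 more than planned.

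In either case, state in Section 14.0 which response definition the 12.5% to 16.4% null rates use. Adding MR to the categories that rule out stable disease in Section 12.0 would be a sensible tidy-up; it does not affect a PR-or-better primary count.

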3.0 BACKGROUND AND RATIONALE

3.1 Overview on Upfront Treatment of Multiple Myeloma

Multiple myeloma (MM) is a disease characterized by a malignant plasma cell proliferation, bone destruction and immunodeficiency. Median age at diagnosis is approximately 70 years. It is responsible for about 1 percent of all cancer-related deaths in Western Countries.¹⁻³ The disease accounts for an estimated 15,000 new cancer cases per year in the United States, as well as approximately 11,000 deaths². Based on the United Kingdom (UK) Myeloma Forum and the Nordic Myeloma Study Group recommendations¹ and National Comprehensive Cancer Network (NCCN) Practice Guidelines⁴, chemotherapy is indicated for the management of myeloma presenting with myeloma-related organ damage (referred to as *symptomatic* myeloma as opposed to *asymptomatic* myeloma). Standard first line treatment for patients with symptomatic multiple myeloma deemed eligible for transplantation, consists of 2 phases of treatment: The first is referred to as the *initial* therapy and consists of various combinations of therapeutic agents. The second consists of high dose melphalan followed by autologous stem cell transplant (HDM/ASCT)^{5,6}. Attempts to *cure* myeloma through high-dose therapy followed by autografting or even allografting have largely failed due to both relapsed disease and treatment-related mortality (TRM). Although high-dose therapy with autologous transplantation is safe and has low TRM (< 5%), it is associated with a continuing and nearly universal risk of disease relapse and progression. Therefore, despite the potential benefits of newer treatments, multiple myeloma

MEMORIAL SLOAN-KETTERING CANCER CENTER IRB PROTOCOL

IRB#: 11-107A(12)

remains an incurable disease and relapse occurs in almost all patients, with a median survival period of 5 to 7 years^{5,6}.

3.1.1 Initial therapy

The regimens currently recommended in the NCCN guidelines for initial therapy of MM in patients who are candidates for HDM/ASCT include dexamethasone, thalidomide and dexamethasone, Lenalidomide and dexamethasone, liposomal doxorubicin. Vincristine and dexamethasone (DVD), as well as several bortezomib based regimens⁴. In previously untreated patients, bortezomib has shown activity as a single agent⁷⁻⁹ and also in combination with dexamethasone^{7,10}, thalidomide/dexamethasone^{11,12}, melphalan/prednisone (MP)^{13,14}, dexamethasone and adriamycin^{15,16} as well as Lenalidomide and dexamethasone. It is widely accepted that in patients who will undergo HDM/ASCT, melphalan-containing regimens should be avoided since stem cell collection may be subsequently hampered.

3.1.2 Autologous Stem Cell Transplantation

There have been two large prospective trials in France (IFM 90) and in UK (MRC 9), and one large retrospective study of myeloma patients in Nordic countries, showing a survival benefit for HDM/ASCT compared to conventional chemotherapy¹⁷⁻¹⁹. In the larger study, IFM 90, newly diagnosed untreated patients less than 65 years of age with DS stage II or III MM were randomized to either SCT after up to 6 cycles of VMCP alternating with BCNU, vincristine, doxorubicin and prednisone (BVAP) or conventional chemotherapy with 18 cycles of VMCP alternating with BVAP. The SCT regimen was MEL 140 mg/m² and TBI, and recombinant interferon alpha (IFN α) was administered to patients in both groups until relapse. By intent-to-treat, SCT patients had a significantly higher response rate (CR+VGPR 38% versus 14%) than those receiving conventional chemotherapy. At a median follow-up of 37 months in the chemotherapy group and 41 months in the SCT group, the latter had significantly longer PFS and OS. The other two studies have confirmed these results although the dose of melphalan given was 200 mg/m² and radiation therapy was not used. Based on these trials, autologous stem cell transplantation using melphalan 200 mg/m² has become part of the standard treatment of symptomatic multiple myeloma. Smaller studies have reached similar conclusions^{6,20}.

Although HDM/ASCT has improved response rate^{6,17,18,20} and overall survival^{17,18,20,21} rate in patients with MM, all patients eventually relapse. Clinical trials have investigated the use of consolidation²² and maintenance²³⁻²⁶ therapy post-transplant to extend the duration of response.

